5. STUDY DESIGN

5.1. Overall Design

This is a long-term, open-label study to evaluate the safety and tolerability of SAGE-718 in rollover or de novo participants with premanifest or early manifest HD.

Participants will be adults with genetically confirmed expansion of the cytosine adenine guanine (CAG) trinucleotide repeat within the huntingtin gene who meet the eligibility criteria. An adult study partner is optional but highly recommended for each participant to support completion of study activities and to answer questions about the participant's condition. For prospective participants and study partners, the study will begin with the informed consent process.

There will be 3 cohorts of participants:

- Cohort 1 (Direct rollover), that includes rollover participants from 718-CIH-201/202 studies, for which 718-CIH-301 informed consent date is \leq 7 days after the last day of the corresponding parent study, and who had previously met the corresponding parent studies' eligibility criteria.
- Cohort 2 (Gap rollover), that includes rollover participants from 718-CIH-201/202 studies, who have experienced a gap of $>$ 7 days between completion of the corresponding parent study and signing of the 718-CIH-301 informed consent and who had previously met the corresponding parent studies' eligibility criteria.

Cohort 1 and 2 include participants who exhibited a measurable functional impairment ($6 < \text{TFC} < 13$) and cognitive impairment (Montreal Cognitive Assessment [MoCA] < 26) at the time of screening for the parent study.

- Cohort 3 (De novo), that includes de novo participants not previously included in a SAGE-718 clinical study. Enrollment of this cohort allows for assessment of the effect of SAGE-718 in a population who does not exhibit measurable functional impairment (TFC=13 [with MoCA ≤ 25]) or meets the criteria of normal cognitive performance (MoCA > 25 [with TFC ≤ 12]) (one or the other; not both). These participants must meet additional 718-CIH-301 study eligibility criteria for de novo cohort outlined within this protocol.

Data from these 3 cohorts will contribute to a comprehensive safety database in a broadly defined group of individuals affected by HD. Data in this study will be collected through the Follow-up Visit.

[figure not shown]

Protocol amendment 2 allowed the duration of participation to be extended from up to 1 year to up to 4 years and provided a path to resume treatment for participants who completed study (through Day 395 visit) under Protocol Version 2 ("718-CIH-301 v2 Completers") or

completed treatment (through Day 365 visit) but did not yet have a Day 395 visit. Participants who have completed their Day 395 visit under Protocol Version 2 and wish to continue participation under Protocol Version 3 or higher ("718-CIH-301 v2 Completers") will return to the site for a Re-Qualification Visit up to 28 days prior to resuming IP at their Next Scheduled Study Treatment Visit (relative to the date of their Day 1 visit. Relevant inclusion and exclusion criteria will be re-confirmed at the Re-Qualification Visit, and participants will re-consent to study participation prior to continuing in the study. Thirty (30) days after resuming IP at their Next Scheduled Study Treatment Visit, 718-CIH-301 v2 Completers will return to the site for a Post Re-Qualification Safety Check-in visit to evaluate safety.

Participants who have completed their Day 365 visit but not their Day 395 visit under Protocol Version 2 when Protocol Version 3 or higher is implemented will NOT be considered "718-CIH-301 v2 Completers". Instead, these participants will return to the site as soon as possible for a Study Continuation Visit during which they will consent to Protocol Version 3 or higher, complete safety assessments, and be dispensed SAGE-718 to resume study treatment. They will continue their study visits per in [Table 3](#) and will not have a Day 395 visit.

Figure 1: Study Schematics

Abbreviation: [REDACTED]

^a De novo and gap (>7 days) rollover participants only. For direct (≤7 days) rollover participants, results of selected last parent study assessment to be used as Day 1 assessments when applicable.

^b The Safety Follow-Up Visit will take place 30 days (±7 days) after the Month 48 or ET visit.

5.1.1. Screening Period

Screening assessments will be performed to determine eligibility for the de novo cohort with premanifest or early manifest HD, as specified in [Table 5](#). The participants who rollover from the parent studies 718-CIH---201/202 with >7 days gap will confirm their eligibility

and undergo selected screening/baseline assessments, as specified in **Table 5**. For the participants who rollover directly from the parent studies 718-CIH-201/202, the results of selected assessments will be carried over from the parent studies to 718-CIH-301 study, as specified in **Table 6**.

5.2. Sample Size and Study Power

This is a long-term, open-label, safety study; there is no formal sample size calculation. The total target enrollment is 300 participants including rollover subjects and the de novo cohort.

5.3. Randomization

Study 718-CIH-301 is an open-label design, hence randomization does not apply.

5.4. Blinding and Unblinding

All participants who receive any IP in this study will receive SAGE-718 in an open-label manner; hence blinding/unblinding does not apply.

6. MODIFICATIONS

6.1. Modifications from the Approved Clinical Study Protocol

This SAP only details the statistical analyses necessary for the synoptic report, focusing on primary endpoints at visits Day 1, Day 90, Day 180, Day 365 and ET.

Cohort 3 (De novo) are not enrolled and therefore will not be included.

6.2. Modifications from the Approved Statistical Analysis Plan

This is the first version of the SAP for the final analysis.

6.3. Modifications from the Approved DMC Charter

Not applicable.

7. ANALYSIS SETS

7.1. Enrolled Set

The Enrolled Set is defined as all subjects who signed the informed consent form (ICF) and are not a screen failure.

7.2. Safety Set

The Safety Set is defined as all participants who were administered investigational product (IP) during the study and will be used to describe the safety data.

8. STATISTICAL ANALYSIS

8.1. General Considerations

Continuous data will be summarized with the number of participants (n), mean, standard deviation (SD), minimum, and maximum. The minimum and maximum will be reported to the same number of decimal places as the raw data recorded in the database. The mean and median will be reported to one more decimal place, and the SD (and the standard error [SE], if applicable) will be reported to two more decimal places, than the raw data recorded in the database. In general, the maximum number of decimal places reported will be four for any summary statistic. Any values that require transformation to standard units (metric or SI) will be converted with the appropriate corresponding precision.

Categorical data will be summarized with the number of participants providing data at the relevant time point (n), frequency counts and percentages. Percentages will be reported to one decimal place unless otherwise specified. Any planned collapsing of categories will be detailed in the SAP text and the data displays.

Percentages will not be presented for zero counts. Percentages will be calculated using the number of participants (n) in the respective analysis set as the denominator. A missing category shall be included only for categorical variables where no data is available. The missing category will be omitted if there are no missing values for that variable.

For the laboratory results that are “ $\leq x$ ” or “ $\geq x$ ”, where x is a number as collected in the data, the numeric part of the result will be used in the calculation in the summary tables. If a laboratory value contains ‘y <’ then y minus 0.1 for values measured to the first decimal place, 0.01 for values measured to the second place, 0.001 for values measured to the third decimal place, and so on, will be used for the analysis. If a laboratory value contains ‘z >’ then z plus 0.1 for values measured to the first decimal place, 0.01 for values measured to the second place, 0.001 for values measured to the third decimal place, and so on, will be used for the analysis. The same is true if the result is presented as below limit of quantification (BLQ) and a lower limit of quantification (LLOQ) value is provided – LLOQ value will be used for calculation in the summary tables. The actual results as collected will be displayed in the listings.

P-values greater than or equal to 0.0001, in general, will be presented to four decimal places. P-values less than 0.0001 will be presented as “<0.0001”. P values greater than 0.9999 will be presented as “>0.9999”.

Confidence intervals will be presented to one more decimal place than the raw data.

All analyses and summary outputs will be presented by cohort: Cohort 1 (Direct rollover), Cohort 2 (Gap rollover), and overall.

All participant data, including those derived, to support tables and figures will be presented in the participant data listings. In general, the participant data listings will be sorted by participant number and assessment visit and date (and time, if applicable).

General definitions are provided below:

- Baseline is defined as the last non-missing measurement prior to the first dose of IP in the current study, unless stated otherwise. If the time of an assessment is collected, baseline will be the latest assessment prior to first dose of IP administration time; if the time of an assessment is not collected, the assessment on Day 1 is assumed to be prior to dosing if the protocol mentions that this assessment needs to be before dosing or it is collected as “pre-dose”.

For Cohort 1 (Direct Rollover), there is no screening period, instead carry-over results of the last assessments from parent studies (CIH-201/202) when applicable, which constitute the baseline or screening assessment for the cohort. For Cohort 2 (Gap Rollover), parent study data will be also carried over to comprise baseline or screening assessment for demographics and baseline characteristics as applicable.

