8.3.2. Clinical Laboratory

Clinical laboratory assessments will include blood samples for hematology, clinical chemistry, coagulation, and urinalysis. Analytes to be evaluated are summarized in [Table 4](#).

All laboratory values will be summarized for the Safety Set by cohort and overall. Results of continuous hematology, clinical chemistry parameters, coagulation, and urinalysis parameters (quantitative) at each scheduled visit and mean changes from baseline will be summarized using standard international (SI) units. In addition, it will also include the summary of anytime on treatment, last values on treatment and last value on study.

All laboratory results will be listed in individual participant data listings.

Results from Hepatitis B and C screening tests, HIV-1 and -2 antibody, CAG test, FSH test at Screening will be listed separately by participant.

Results from urine drug test pregnancy test will be listed separately by participant.

Normal ranges for each parameter will be provided by the laboratory.

Table 4: Summary of Clinical Laboratory Analytes

Biochemistry	Renal Panel: glucose, calcium, phosphorus, blood urea nitrogen, creatinine, sodium, potassium, chloride, bicarbonate Hepatic Panel: albumin, alanine aminotransferase, alkaline phosphatase, aspartate aminotransferase, total bilirubin, direct bilirubin, indirect bilirubin, total protein, lactate dehydrogenase, gamma glutamyl transferase Other: triglycerides, cholesterol (low density lipoprotein [LDL], high density lipoprotein [HDL]), creatine phosphokinase, TSH and reflex to free T3/T4 if TSH is abnormal
Hematology	Red blood cell (RBC) count, hemoglobin, hematocrit, white blood cell count with differential, platelet count, RBC indices (mean corpuscular volume [MCV], mean corpuscular hemoglobin [MCH], and mean corpuscular hemoglobin concentration [MCHC]).
Urinalysis	Protein, glucose, pH, blood, leukocyte esterase, urobilinogen, bilirubin, ketones, nitrite
Coagulation	Activated partial thromboplastin time, prothrombin time, and international normalized ratio
Serology (screening only for Cohort 2 and 3)	Hepatitis B and C screening tests, HIV-1 and -2 antibody

Liver function tests will be monitored closely for potentially clinically significant PCS values, and will be summarized for occurrence anytime post-baseline for the following parameters for these PCS threshold (for condition involving more than one parameter, the results need to be from the same timepoint):

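### SAP 8.1 gives two values to the same below-limit laboratory result: '<y' is analysed as y minus one reporting unit, but BLQ with LLOQ = y is analysed as y

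*SAP*

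**What the plan says.** SAP Section 8.1 (General Considerations) has three substitution rules for laboratory results that are not plain numbers.

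- **'≤x' and '≥x':** "the numeric part of the result will be used in the calculation in the summary tables".
- **'<y' and '>z':** for '<y' the rule is "then y minus 0.1 for values measured to the first decimal place, 0.01 for values measured to the second place", continuing in the same pattern for further decimals. For '>z' one unit is added instead.
- **BLQ:** "The same is true if the result is presented as below limit of quantification (BLQ) and a lower limit of quantification (LLOQ) value is provided". After a dash, the sentence gives the value: "LLOQ value will be used for calculation in the summary tables".

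The section adds that listings will show results as collected, so only the summary tables are affected.

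The substituted numbers feed the laboratory summaries in Section 8.3.2, where results "at each scheduled visit and mean changes from baseline will be summarized using standard international (SI) units". Change from baseline in laboratory parameters is one of the primary endpoints (SAP Section 4.1). For Cohort 1, Section 8.1 takes as baseline the "carry-over results of the last assessments from parent studies (CIH-201/202) when applicable, which constitute the baseline or screening assessment for the cohort". SAP Table 6 agrees: safety laboratory results are in the carry-over column, none is scheduled on Day 1, and the first sample in this study is at Day 30.

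**The concern.** A result of '<0.5' and a result of BLQ with LLOQ 0.5 say the same thing about the sample. Under Section 8.1 the first is analysed as 0.4 and the second as 0.5. A programmer following the text would code both rules and so make the analysed value depend on how the laboratory or database wrote the result.

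In Cohort 1, baseline and follow-up come from different studies, so a difference in format between the two sources would be subtracted as if it were a change in the participant. There is no control arm in which the same artefact could be recognised.

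**Working it through.** The documents give no figure to reproduce here, and no limit of quantification for any analyte. The check applies the two rules to assumed limits.

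**Inputs**
- Rule A, '<y' with d reported decimals (SAP 8.1): A(y) = y − 10^(−d).
- Rule B, BLQ with LLOQ = y (SAP 8.1): B(y) = y.
- Limits y: assumed, shown over a range.
- Share f of a cohort that is below the limit at both times and switches format in the same direction: assumed, shown over a range.

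**Step 1. Difference for one result.** B(y) − A(y) = 10^(−d), always exactly one reporting unit.

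| Assumed limit | '<y' becomes | BLQ becomes | Difference | Share of limit |
|---|---|---|---|---|
| 5.0 | 4.9 | 5.0 | 0.1 | 2% |
| 1.0 | 0.9 | 1.0 | 0.1 | 10% |
| 0.5 | 0.4 | 0.5 | 0.1 | 20% |
| 0.2 | 0.1 | 0.2 | 0.1 | 50% |
| 0.1 | 0.0 | 0.1 | 0.1 | 100% |
| 0.05 | 0.04 | 0.05 | 0.01 | 20% |
| 0.005 | 0.004 | 0.005 | 0.001 | 20% |

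**Step 2. Change from baseline for one participant.** With '<y' at baseline and BLQ at follow-up, the derived change is B(y) − A(y) = +1 unit. In the reverse order it is −1 unit. If the format is the same at both times it is 0.

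**Step 3. Shift in the cohort mean change.** Shift = f × one unit. With a limit of 0.1 (unit 0.1):
- f = 5%: 0.05 × 0.1 = 0.005
- f = 25%: 0.25 × 0.1 = 0.025
- f = 100%: 1 × 0.1 = 0.1

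**Step 4. Can the wording be read consistently?** The opening of the BLQ sentence has no clear antecedent. If it points to the adjacent '<' and '>' rules, the words after the dash contradict it. If it points back to the '≤x' rule, the sentence is consistent in itself but conflicts with the '<y' rule. The explicit instruction is the LLOQ under either reading.

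**Step 5. Liver thresholds (SAP 8.3.2).** These are multiples of ULN, almost all exceeded from below. A below-limit value does not reach them under either rule. The one '<' condition, alkaline phosphatase below 2×ULN, is met under either rule. The counts do not change.

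**Step 6. After alignment.** If BLQ is also set to y − 10^(−d), the difference in Step 1 is 0 for every limit recorded to the same number of decimals, and Steps 2 and 3 give 0.

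**The case against.** The strongest reply is that the false change is hypothetical. It needs the same analyte to be stored as '<y' at one time and as BLQ at another. Nothing in the documents says that any analyte in SAP Table 4 is returned as BLQ, or that the parent studies and 718-CIH-301 differ in laboratory, unit or format. Cohort 2 has its own Screening and Day 1 safety laboratory samples (SAP Table 5), so the cross-study route does not arise there. This stands.

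The stakes are also low. SAP Section 2 describes a purely descriptive analysis for a synoptic report of a terminated study, and the artefact is one last-digit unit. This stands too.

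It can further be said that the decrement and increment are defensible. They keep '<y' below y and '>z' above z, which matters for the normal-range shifts in SAP Table 2 and for strict '>' thresholds. Replacing them with the limit itself, or objecting that '<0.1' becomes zero, would be a preference. This is right, and it narrows the fix to the BLQ sentence.

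Two further gaps are missing detail rather than contradictions. The text refers to the number as collected, which points to the recorded unit, but it does not state the order of substitution and SI conversion. The substitution for whole-number limits is unspecified.

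None of this removes the conflict between the two rules.

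**Conclusion.** The inconsistency is real and lies in the text itself: equivalent results receive y minus one unit and y. The size is exactly one reporting unit per affected participant, which is 2% to 100% of the limit for assumed limits of 5.0 down to 0.1. The cohort mean change shifts by the affected share times that unit.

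Any effect on the tables rests on an assumption that the documents neither confirm nor exclude, namely that both formats occur for one analyte. The carry-over in Cohort 1 makes this possible but does not show it.

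A reader might infer that a primary endpoint is biased, or that the whole of Cohort 1 would show a change that did not happen. The documents do not support either inference. Only participants below the limit whose format differs between baseline and follow-up are affected. The liver multiples-of-ULN counts do not move, and the listings keep the results as collected. This is a low-severity correction of wording.

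**What to change.** Reword the BLQ sentence in SAP Section 8.1 so that BLQ with LLOQ = y takes the same value as '<y', which under the existing rule is the LLOQ minus one reporting unit. State that the substitution is made in the unit as collected, before SI conversion, and identically for parent-study and 718-CIH-301 records. The reporting unit should be taken from the same number of decimals in both sources, because a limit held as 0.1 in one and 0.10 in the other would give 0.0 and 0.09. Leave the '>z' and '≤x'/'≥x' rules as they are.

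The cost is one reworded sentence and a small change to the derivation program, with no new data. If the database is already locked, SAP Section 2 gives the route: document and discuss the change in the CSR.

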Safety laboratory assessments ^k	X		X		X	X	X	X
Urine drug test		X ^f	X	X	X	X		X
Alcohol breath test		X ^f	X	X	X	X		X
Cigarette/tobacco use assessment		X ^f	X	X	X	X		X
Pregnancy test ^l	X		X		X	X	X	X
REDACTED								
C-SSRS (Since Last Visit)		X		X	X	X	X	X

Assessments	Carry-over Results of the Last Assessments from Parent Studies when Applicable ^{a,f}	Treatment Period						
		Day 1	Day 30 (±7 days)	Day 60 (±7 days)	Day 90 (±7 days)	Day 180 (±14 days)	Day 270 (±14 days)	Day 365 (±14 days) ^b
UHDRS ^p	X							
MoCA	X							
IP self-administration ^w					X (once daily in the morning)			
IP dispensation ^x		X	X	X	X	X	X	X
IP accountability/return ^y			X	X	X	X	X	X
IP adherence monitoring					X			
AEs/SAEs ^z					X			
Prior and concomitant medications and procedures/therapies ^{aa}					X			

Abbreviations: AE = adverse event, CAG = cytosine-adenine-guanine trinucleotide repeat within the huntingtin gene, [REDACTED]; COVID-19 = coronavirus disease 2019; C-SSRS = Columbia–Suicide Severity Rating Scale; ECG = electrocardiogram; eCRF = electronic Case Report Form, FSH = follicle-stimulating hormone; [REDACTED]; HD = Huntington's Disease; [REDACTED]; HIV = human immunodeficiency virus; IP = investigational product; MoCA = Montreal Cognitive Assessment; [REDACTED]; SAE = serious adverse event; [REDACTED]; UHDRS = Unified Huntington's Disease Rating Scale; [REDACTED].

NOTE: Any additional parent study data needed to support the 718-CIH-301 data or analyses will be carried over from the applicable parent study.

- ^a The carryover assessments constitute the baseline/screening assessments for this extension study.
- ^b Participants who have completed their Day 395 visit under Protocol Version 2 and wish to continue participation under Protocol Version 3 or higher (“718-CIH-301 v2 Completers”) will return to the site for a Re-Qualification Visit ([Table 4](#)) up to 28 days prior to resuming IP at their Next Scheduled Study Treatment Visit (relative to the date of their Day 1 visit, see [Table 5](#)).
- ^c Both participants and study partners (if applicable) will be consented on Day 1. A legally authorized representative may consent on behalf of participants who are not capable of providing informed consent in the opinion of the investigator. [REDACTED]

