7. INVESTIGATIONAL PLAN

7.1. Overall Study Design

This is a long-term, open-label study to evaluate the safety and tolerability of SAGE-718 in rollover participants from Phase 2 placebo-controlled studies and de novo participants with premanifest or early manifest HD.

Participants will be adults with genetically confirmed expansion of the cytosine-adenine-guanine (CAG) trinucleotide repeat within the huntingtin gene, who meet the eligibility criteria. An adult study partner is optional but highly recommended for each participant to support completion of study activities and answer questions about the participant's condition. For prospective participants and study partners, the study will begin with the informed consent process.

There will be 3 cohorts of participants:

- Cohort 1 (Direct rollover) includes rollover participants from the 718-CIH-201 and 718-CIH-202 studies for whom 718-CIH-301 informed consent date is \leq 7 days after the last day of the corresponding parent study and who had previously met the corresponding parent studies' eligibility criteria.
- Cohort 2 (Gap rollover) includes rollover participants from the 718-CIH-201 and 718-CIH-202 studies who have experienced a gap of $>$ 7 days between completion of the corresponding parent study and signing of the 718-CIH-301 informed consent and who had previously met the corresponding parent studies' eligibility criteria.

Cohorts 1 and 2 include participants who exhibited a measurable functional impairment ($6 < \text{TFC} < 13$) and cognitive impairment (Montreal Cognitive Assessment [MoCA] < 26) at the time of screening for the parent study.

- Cohort 3 (De novo) includes de novo participants not previously included in a SAGE-718 clinical study. Enrollment of this cohort allows for assessment of the effect of SAGE-718 in a population that does not exhibit measurable functional impairment ($\text{TFC}=13$ [with MoCA ≤ 25]) or that meets the criteria of normal cognitive performance ($\text{MoCA} > 25$ [with $\text{TFC} \leq 12$]) (one or the other; not both). These participants must meet additional 718-CIH-301 study eligibility criteria for the de novo cohort outlined within this protocol.

[figure not shown]
Data from these 3 cohorts will contribute to a comprehensive safety database in a broadly defined group of individuals affected by HD. Data in this study will be collected through the Safety Follow-up Visit.

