8.3. Safety Analysis

Safety and tolerability of SAGE-718 is the primary objective of this study. Proportion of participants experiencing treatment-emergent adverse events (TEAEs) and severity of TEAEs, number of participants who withdraw due to AEs, and change from baseline in vital signs, clinical laboratory analyses, electrocardiograms (ECGs), and responses on the Columbia–Suicide Severity Rating Scale (C-SSRS) are the primary endpoints.

The Safety Set will be used for all safety summary tables by cohort and overall.

The safety endpoints and variables considered in the summary tables for this study are summarized in [Table 2](#).

Table 2: Safety Endpoints and Variables in the Summary Tables

Safety Evaluation	Incidence	Raw Value	Change from Baseline	Normal Range Shift from Baseline	Potentially Clinically Significant	Abnormality/ Clinical Significance
Adverse Events	X					
Clinical Laboratory (Chemistry, Liver function, Hematology,		X*	X	X	X	

Safety Evaluation	Incidence	Raw Value	Change from Baseline	Normal Range Shift from Baseline	Potentially Clinically Significant	Abnormality/Clinical Significance
Coagulation, Urinalysis)						
Physical Exam		*				
Vital Signs		X	X		X	
ECG		X	X		X	*
C-SSRS	X	X		X		

ECG = Electrocardiograms; C-SSRS = Columbia–Suicide Severity Rating Scale
 X = Safety Assessment will be summarized in tables
 * = Safety Assessment will be listed in individual participant data listings

Anytime on treatment, last value on treatment and last value on study will be included in the summaries whenever indicated in the relevant sections as following: Anytime on treatment is defined as measurement on or after first dose, on or before the date of last dose. Last value on treatment is defined as the last post-baseline value between first dose of IP (exclusive) and up to the date of last dose of IP (inclusive). Last value on study is defined as the last post-baseline value on or after the first dose of IP and on or before the last date of the study.

The safety variables evaluated at scheduled visits are taken as done in nominal visit, without any windowing. If a value is available for a nominal scheduled visit, that value will be used in summary by visit. If scheduled visit value is not available, a value from the specific visit window will be included in summary.

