8.3.1. Adverse Events

An AE is any untoward medical occurrence in a patient or clinical investigation participant and that does not necessarily have a causal relationship with this treatment. An AE can therefore be any unfavorable and unintended sign (including an abnormal laboratory finding), symptom or disease temporally associated with the use of a medicinal (investigational) product whether or not related to the medicinal (investigational) product. In clinical studies, an AE can include an undesirable medical condition occurring at any time, including baseline or washout periods, even if no study treatment has been administered.

Adverse events will be coded using Medical Dictionary for Regulatory Activities (MedDRA) Version 25.1.

A TEAE is defined as an AE with onset on or after the first dose of SAGE-718- - either in the parent study or within this protocol and on or after the ICF sign off date. For more clarification, a TEAE is defined as below:

- For Placebo rollover participants from parent study: TEAE is defined as an AE with onset on or after the first dose of SAGE-718 in this protocol.

- For SAGE-718 rollover participants from the parent study: TEAE is defined as an AE with onset on or after the ICF sign off in this protocol.

Pre-treatment AE is defined as below.

- For Placebo rollover participants from parent study: Pre-treatment AE is defined as an AE with onset before the first dose of SAGE-718 in this protocol and after ICF sign off date in this protocol or ongoing AE from parent study.
- For SAGE-718 rollover participants from the parent study: Pre-treatment AE is defined as an AE with onset after ICF sign off date in this protocol and before the first dose date of IP in the current protocol.

On-treatment TEAE:

- For Placebo rollover participants from parent study: On-treatment TEAE is defined as an AE with onset on or after the first dose of SAGE-718 in this protocol and on or before IP last dose date + 30 days (Note that time does not matter for the end of this period. i.e. if AE occurred after the last dose but on the same date of last dose, it is considered as on-treatment TEAE).
- For SAGE-718 rollover participants from the parent study: On-treatment TEAE is defined as an AE with onset on or after first IP dose date/time and on or before IP last dose date + 30 days.

Post-treatment TEAE: AE onset date on or after IP last dose date + 31 days.

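### Change-from-baseline and shift tables mix prior-placebo and prior-SAGE-718 rollovers; parent-arm columns would be a cheap improvement, and one sentence on the C-SSRS baseline needs a minor correction

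*SAP*

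**What the plan says.** Protocol 7.1 describes a study of "SAGE-718 in rollover participants from Phase 2 placebo-controlled studies and de novo participants with premanifest or early manifest HD". SAP 6.1 then records that "Cohort 3 (De novo) are not enrolled and therefore will not be included", so every analysed participant is a rollover.

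SAP 8.1 sets the columns: "All analyses and summary outputs will be presented by cohort: Cohort 1 (Direct rollover), Cohort 2 (Gap rollover), and overall". Cohorts 1 and 2 are separated by the time from the end of the parent study to consent (up to 7 days, or more than 7), not by parent treatment. SAP 8.3 repeats the column rule for safety: "The Safety Set will be used for all safety summary tables by cohort and overall". The only baseline subgroups in SAP 8.2.3 are age and sex.

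On baseline, SAP 8.1 states: "Baseline is defined as the last non-missing measurement prior to the first dose of IP in the current study, unless stated otherwise". For direct rollovers, Protocol Table 3 (footnote a) adds: "The carryover assessments constitute the baseline/screening assessments for this extension study".

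Parent arm enters the SAP in 8.3.1: "For Placebo rollover participants from parent study: TEAE is defined as an AE with onset on or after the first dose of SAGE-718" in this study, whereas for prior-SAGE-718 participants the TEAE period starts at consent.

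For the C-SSRS, SAP 8.3.6 takes the worst pre-dose answer, excluding the lifetime version, and says this typically includes a past-12-month version from screening. In the schedules and Protocol 12.1.7, the Screening/Baseline form belongs to Cohort 3 only; rollovers complete Since Last Visit forms.

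**The concern.** Change from baseline in laboratory values, vital signs, ECG and C-SSRS is a primary endpoint, and the synoptic report is confined to primary endpoints, "focusing on primary endpoints at visits Day 1, Day 90, Day 180, Day 365 and ET". With no model in the plan, the table columns are the only place where prior exposure could be separated.

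A drug effect that arose in the parent study and persists to entry is already inside the baseline of a prior-SAGE-718 participant and does not appear as change. The same effect in a prior-placebo participant does. A pooled mean is then neither the change on first exposure nor the change on continued exposure, and the summary tables do not let the reader tell which of the two drives it.

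The C-SSRS matter is smaller. Section 8.3.6 names a component that this study does not schedule for any analysed participant, so a programmer must decide whether a parent form stands in for it. That decision sets how far back baseline looks. The maximum-rank ideation shift compares baseline with the whole post-baseline period, so a short baseline look-back can produce apparent worsening without any drug effect.

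**Working it through.** The plan states no figure to reproduce here. Both calculations are illustrations with assumed inputs.

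**(a) Pooled mean change**

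Let D be the shift from the drug-free level on SAGE-718, f the share of a column previously exposed, and c the share of D still present at entry. Assume no further effect from longer exposure. The documents give none of D, f or c.

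- Prior placebo: change = D.
- Prior SAGE-718: change = (1 − c)D.
- Pooled: (1 − f)D + f(1 − c)D = (1 − fc)D.

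Pooled change as a percentage of D:

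| f | c = 0 | c = 0.5 | c = 1 |
|---|---|---|---|
| 1/3 | 100 | 83 | 67 |
| 1/2 | 100 | 75 | 50 |
| 2/3 | 100 | 67 | 33 |

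The understatement is fc. It is zero if nothing persists.

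**(b) Maximum-rank ideation shift with no drug effect**

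Assume ideation in 1% of participants per month, 365 days of follow-up, and a baseline look-back of d days. Two models for the share with any ideation in d days:

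- Independent months: P(d) = 1 − 0.99^(d/30.4). This gives 0.99% at 30 days, 2.93% at 90 and 11.37% at 365.
- Ideation recurring in the same people (gamma frailty, shape 0.1, same one-month rate): 0.99%, 2.69% and 7.87%.

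Net excess after baseline = P(365) − P(d), in percentage points:

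| Baseline look-back | Recurrent | Independent |
|---|---|---|
| 30 days | 7.87 − 0.99 = 6.9 | 11.37 − 0.99 = 10.4 |
| 90 days | 7.87 − 2.69 = 5.2 | 11.37 − 2.93 = 8.4 |
| 12 months | 0 | 0 |

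The recurrent column is not a lower bound: stronger recurrence or a lower rate reduces it further. The direction follows from unequal look-back; the size follows from the assumptions.

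**The case against.** Reporting by cohort is the protocol's own plan (13.6), and the SAP is a purely descriptive one for a terminated study. Comparison of drug with placebo belongs to the parent studies. That is fair, and it is why this is an improvement to a display rather than a defect in the design.

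A reader might infer that the entry baseline is wrong. The documents do not support that: it is the protocol's rule and is valid for change during this study.

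A reader might also infer that persisting abnormalities are hidden. They are not. SAP Table 2 plans raw values and PCS values for laboratory tests, vital signs and ECG; liver thresholds are absolute multiples of the upper limit of normal; laboratory shift tables show the baseline category; and participant data are listed. Those tables also pool the arms, but an absolute abnormality stays visible. The loss is mainly in mean change and in shifts read as change.

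Persistence may be nil. The documents do not say whether parent-study drug was still being taken at the carried-over visit, Cohort 2 has a gap of more than 7 days by definition, and Protocol 5.1 reports no clinically relevant mean ECG change in completed studies.

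Blinding is no obstacle. Protocol 9.5 keeps participants and site staff blinded to parent treatment during the study, and the TEAE rule already needs parent arm at analysis.

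On the C-SSRS, the worst-pre-dose rule works with whatever forms exist, and the 12-month form appears only in an illustrative sentence. SAP 8.1 also carries the last parent assessments into the Cohort 1 baseline where applicable. So a reader who inferred that the baseline cannot be computed would be going too far. Nor can one infer that the Cohort 1 look-back is at most 7 days: when the last parent visit and Day 1 coincide, a Since Last Visit form may reach back over the preceding parent-study interval.

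**Conclusion.** Part (a) holds as a cheap improvement. Every analysed participant is a rollover, baseline ignores parent arm, and no planned column or subgroup separates the arms, although the arm is already needed elsewhere in the SAP. The pooled mean change understates the drug-naive change by fc, which ranges from 0 to 67% over the values tried. Both inputs are assumed, so a claim that the tables do understate an effect, or by any particular amount, goes beyond the documents. That columns contain both arms follows from the placebo-controlled parents and the separate TEAE rules, not from reported counts.

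Part (b) is minor. The 12-month form has no scheduled source in this study for Cohorts 1 and 2. If only Since Last Visit forms count, the baseline period is shorter than the post-baseline period and the maximum-rank shift can show worsening with no drug effect. Its size rests entirely on assumed ideation rates and is about zero over one year if a 12-month form counts.

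**What to change.** 1. Keep the entry baseline and the cohort columns. In the change-from-baseline and shift tables, add placebo-to-SAGE-718 and SAGE-718-to-SAGE-718 columns under overall.
2. Optionally, for the SAGE-718-to-SAGE-718 group, add change from the parent-study pre-dose baseline.
3. In SAP 8.3.6, replace the sentence on the past-12-month form with the forms that make up baseline for Cohort 1 and for Cohort 2, naming any parent form carried over.
4. Footnote the maximum-rank ideation shift with the look-back length on each side.

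Cost: SAP wording and two columns from a variable already required. The optional supplement also needs records merged from two parent studies.

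The columns are smaller. Actual enrolment is not given. If the planned 128 + 28 = 156 rollovers split evenly, each column has 78, with standard errors √2 ≈ 1.4 times the pooled ones. At 1:2 the columns have 52 and 104, with standard errors √3 ≈ 1.7 and √1.5 ≈ 1.2 times the pooled ones. That is acceptable for descriptive tables.
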